5.7. Subject Status Definitions

Enrolled: All subjects who sign an informed consent will be considered enrolled in the study. All subjects consented on the study will be assigned to the research study in EPIC.

Screen Failure: A subject who is withdrawn or discontinues from the study prior to receiving DBS is considered a screen fail. Screen failures are not considered a study accrual and will be replaced. Note: The IRB defines any individual that has signed an informed consent as an enrollment in this study and so screen failures should be reported to the IRB with enrollment numbers.

On-Study: A subject is considered on-study on the date when the study team has confirmed the subject has met all of the inclusion and none of the exclusion criteria, and the treating physician/surgeon or study PI has signed off on the confirmation.

On-Treatment: A subject is considered on-treatment on the date that the DBS surgery is initiated. A subject who is withdrawn or discontinues from the study after receiving DBS surgery is considered a discontinuation and will not be replaced.

On Follow-up: A subject is considered on follow-up on the date that the DBS surgery is completed.

Off-Study: A subject is considered off-study if they are removed from the study for any of the reasons listed in Section 4.6, or if they have completed all study assessments through follow-up (6 Month follow-up visit).

6. DEVICE INFORMATION

Description

The agent under investigation is an intracerebral infusion of autologous CSF. The autologous CSF will be obtained via lumbar puncture and administered during the same procedure, so there is no need for storage of the CSF.

Agent Preparation and Administration

A lumbar puncture will be performed to obtain 10 ml of autologous CSF. This will be passed through a sterile 0.1 micron filter and maintained sterile. A disposable, MRI-compatible frameless stereotactic system that is employed for MRI-guided DBS surgery under general anesthesia will be secured to the patient's skull. Once the patient is positioned within the MRI, the dura is sharply punctured with a sharp, ceramic stylet, and the MR-compatible infusion catheter is inserted.

The research infusion of autologous CSF is initiated at 5 microliters/minute. Serial MRI monitoring of the infusion is obtained with T2 weighted images at 15 minute intervals until the target nucleus can be visualized or until a total of 500 microliters is administered. Any remaining CSF will be disposed of at the end of the procedure.

A Medfusion 3500 syringe infusion pump with a 1.0 milliliter BD glass syringe will be used with extension tubing (*Medex Micro Bore*, Product Code 536020, Smiths Medical, Dublin, OH, USA). The infusion catheter will be the SmartFlow™ K123605 (MRI Interventions).

7. EVALUATION AND ASSESSMENTS

7.1. Schedule of Events

The following table shows the standard of care and research assessments that will be performed throughout the study.

	Screening and Baseline*	DBS Surgery	One Month (\pm 2 weeks)	6 Months (\pm 1 month)
Informed Consent	X			
Review study eligibility	X			
Medical History	X			
MRI	X	X		
Vital signs	X	X		

PDQ-39*	X			X
Physical Exam	X			
Neurological Exam	X		X	X
Clinical Labs	X			
Lumbar Puncture and CED infusion		X		
Neuropsychological Evaluation	X			X
UPDRS	X			X
Review of PD medications	X			X
Adverse Event assessment		X	X	X

*Screening and Baseline assessments will be performed up to 90 days prior to DBS surgery. Standard of care procedures completed within this period but prior to consent may be used for the purposes of the study. The order of screening/baseline procedures will vary, but all tests required for eligibility must be complete prior to confirmation of eligibility.

Please note that any assessments done as part of the patient's standard care need not be performed by an investigator, as long as the assessor is qualified and regularly performs this type of assessment as part of their regular medical center duties. The results of the standard tests and any abnormal findings will be reported back to the principal investigator to be evaluated and reported for the research.

7.2. Study Assessments

7.2.1. Medical History

A medical history should be obtained during the screening/baseline visit to establish baseline medical condition for evaluation of AEs. Medical history includes clinically significant diseases, surgeries, history of cancer, brain injuries, and heart conditions. A start date (year), end date (year) and any medications or surgeries to treat the condition will be recorded. In addition, all medications (e.g., prescription drugs, over-the-counter drugs, herbal/homeopathic remedies, nutritional supplements) used by the patient at the time of the assessment for any reason will be collected at this time.

7.2.2. MRI

For the purpose of this study, MR Exams without contrast will be performed. The MR Imaging should include T1, T2, and DTI sequences. In addition, MR Images: DWI (including ADC maps, which allows differentiation between lesion cytotoxic edema-low ADC and vasogenic edema around the lesion-high ADC) will be obtained at baseline.

7.2.3. Vital Signs

Vital signs including respiratory rate, pulse rate, systolic blood pressure [SBP], and diastolic blood pressure [DBP] and body temperature, will be collected at Screening/Baseline assessment and during CED infusion. Vital signs will be continuously monitored during the DBS surgery. At the Screening/Baseline visit, it is recommended that vital signs be assessed in subjects who have been in a seated resting position for at least 3 minutes. Transient changes in BP, HR, or RR may be expected. If a subject has symptoms that appear to be related to changes in BP, HR, or RR, all changes deemed by the Investigator to be of clinical importance should be reported as an AE.

7.2.4. PDQ-39 Questionnaire

A self reported Parkinson's Disease Questionnaire (PDQ-39) will be completed at Screening/Baseline as well as 6 Months FU as a secondary measure of effectiveness.

7.2.5. Physical Exam

A full physical examination will be performed at the Screening/Baseline visit only. Physical examinations will include examination of the following body systems: general appearance (including height and body weight), skin, neck, HEENT (head, ears, eyes, nose and throat), heart (auscultation of heart sounds), lungs (auscultation of lung fields), abdomen palpation and auscultation of bowel sounds, lymph nodes, extremities, and nervous system.

An abbreviated, symptom-directed physical exam will be performed at all other assessments. Any abnormal findings which were not noted at the baseline assessment must be reported as an AE.

7.2.6. Neurological Exam

A full neurological exam will be performed at the Screening/Baseline visit and at the 1 and 6 Month follow up visits for adverse event determination. Neurological examinations will include orientation, sensory (pain, position, vibration, and light touch), reflexes (biceps, triceps, knees, ankles and pathological). Coordination and balance will be tested by performing Finger to Nose, Heel to Shin, Rapid Alternating Movements, Heel-to-toe walking, and Romberg's test assessments. In addition, motor, strength and gait testing will be performed.

7.2.7. Laboratory Parameters

Blood samples for clinical labs will be obtained at the Screening/Baseline visit to determine eligibility for DBS surgery. The following clinical laboratory tests should be performed as per standard of care:

Hematology

- Hemoglobin
- Hematocrit
- Total leukocyte count and differential
- Platelet count

Serum Chemistry

- Aspartate aminotransferase (AST)
- Alanine aminotransferase (ALT)
- Gamma-glutamyl transferase (GGT)
- Total bilirubin
- Direct bilirubin
- Alkaline phosphatase
- Lactate dehydrogenase (LDH)
- Creatinine
- Blood urea nitrogen (BUN)
- Blood glucose
- Sodium
- Potassium
- Chloride
- Bicarbonate
- Calcium

- Phosphorus

Clotting Time

- Prothrombin time (PT)
- Partial Thromboplastin Time (PTT)

Pregnancy Test

7.2.8. Neuropsychological Assessment

A standard neuropsychological assessment will be conducted prior to DBS surgery and will be repeated at the 6 month follow up visit for potential cognitive and psychological effects of the surgery.

7.2.9. Unified Parkinson's Disease Rating Scale

The Unified Parkinson's Disease Rating Scale (UPDRS) will be performed at Screening/Baseline, and at the 6 Month Follow Up visit to assess the patient's motor symptoms. Each treated subject will be examined "off medication" and "on medication" by a qualified movement disorders specialist.

7.3. Final Study Visit

The final study visit will occur at the 6 Month Follow Up visit. All final efficacy assessments will be collected at this visit. Any ongoing adverse events will be followed at the routine annual clinic visit.

7.4. Early Termination Visit

In the event that a subject does not want to continue in the study until the 6 Month Follow Up visit, every effort will be made to complete a visit where final AE determination will be made. Subjects may withdraw voluntarily from participation in the study at any time. The subject will continue to be monitored on an annual basis as part of routine clinical care.

8. DATA ANALYSIS PLAN

For this study, the Safety and Effectiveness assessment will be descriptive with no statistical endpoints. The results will be examined and analyzed and used as a basis for determining the nature of future studies. Formal hypothesis testing for efficacy is not proposed for this initial safety and preliminary efficacy trial.

8.1. Safety

The PI will evaluate all AE's that occur throughout the study and provide his assessment of the study safety profile as well as his recommendations for the study continuation. All AEs will be communicated to the FDA as part of the annual reporting for this proposed IDE study.

All AEs will be reported and categorized by investigators as definitely, probably, possibly, unlikely, or unrelated to the CSF infusion, and/or Parkinson's disease progression. Standard Code of Federal Regulation definitions for Serious Adverse Events (SAEs) and Unanticipated Adverse Device Effects (UADEs) will be used in assessment of AEs.

Primary safety endpoint for this study is the adverse event profile generated during the CED procedure through Month 6.

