4. SUBJECT ELIGIBILITY

Patients with medically-refractory Parkinson's disease who are planned for MRI-guided DBS surgery under general anesthesia are candidates for this protocol. They will be invited to participate in this study if they decide to have DBS surgery in the intraoperative MRI suite under general anesthesia. Patients who decide to have awake DBS surgery with clinical and electrophysiologic testing will not be eligible. The consenting process will occur in the outpatient clinic setting, and patients will have the opportunity to review the consent document at home with their families. A total of eight patients will be enrolled.

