5. TREATMENT PLAN

5.1. Study Overview

This will be an open-label, single-arm, pilot study investigating the safety and feasibility of infusion-enhanced, MRI-guided DBS electrode placement. We intend to enroll patients, with Parkinson's disease and medically-refractory motor symptoms, who are already planned for MRI-guided DBS electrodes under general anesthesia. The *hypothesis* of the study is that a convective micro-infusion of autologous CSF will enhance the T2-weighted MRI visualization of the targeted nucleus during image-guided DBS surgery for Parkinson's disease. We will record standard clinical measures of PD at baseline and 6 months following DBS surgery. The study will recruit patients at a rate of approximately one a month and will take less than two years to complete.

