8.4. Statistical Considerations and Sample Size

This is an open-label feasibility study of 4 subjects to be recruited from a single center. In order to find 4 eligible subjects suitable for treatment, up to 20 subjects may be consented and screened. For this study, a statistical sample size analysis is not proposed. All those subjects that were consented and then found not meeting study requirements will be considered screen failures.

The Safety and Effectiveness assessment will be descriptive with no statistical endpoints. The results will be examined and analyzed and used as a basis for determining the nature of future studies.

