9.4.2. Data Safety Monitoring Plan

The Principal Investigator will provide continuous monitoring of subject safety in this trial.

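### No step ties each new infusion to the previous subject's one-month neurological exam, so the continuation judgement can be made without it

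*Combined protocol and SAP*

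**What the plan says.** Safety is the primary objective (section 3.1). Section 8.1 makes the PI responsible for evaluating adverse events and says he will "provide his assessment of the study safety profile as well as his recommendations for the study continuation". Section 9.4.2, the whole data safety monitoring plan, is one sentence: "The Principal Investigator will provide continuous monitoring of subject safety in this trial". Neither section says when a continuation recommendation is made or what data must be in hand.

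Section 7.2.6 places full neurological exams at baseline and "at the 1 and 6 Month follow up visits for adverse event determination". The schedule in section 7.1 gives the one-month visit a window of two weeks either side and has no outpatient visit before it.

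On pace, section 5.1 says: "The study will recruit patients at a rate of approximately one a month and will take less than two years to complete". Section 5.7 counts a subject as enrolled at consent, and section 5.5 lets screening and baseline take up to 90 days before surgery. The interval between infusions is therefore not fixed by the recruitment rate. On size, section 8.4 says "This is an open-label feasibility study of 4 subjects to be recruited from a single center", whereas section 4 says "A total of eight patients will be enrolled".

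**The concern.** Section 9.5 names neuronal damage as the main risk of the infusion, with possible loss of sensation, weakness or worse movement symptoms. The exam in section 7.2.6 tests these functions, and the plan says it is for finding adverse events. The animal work also looked at tissue at 28 days for late toxicity (section 2.4.2), so the sponsor itself treats about one month as an informative time.

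If that exam can fall after the next infusion, the judgement promised in section 8.1 can be made without the first structured look at the risk that matters most. Stimulation is switched on at one month and then adjusted together with medication (section 5.3.5), so findings after that are harder to attribute to the infusion. With so few subjects, each transition is a large share of the study.

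**Working it through.** No alpha, power or effect size is stated, so the check is calendar arithmetic, with 1 month = 30.4 days.

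**Inputs.** Recruitment about 1 a month, total under 24 months (5.1); 4 subjects (8.4) or 8 (section 4); first scheduled neurological exam at 1 month, 14 days either side (7.1, 7.2.6); up to 90 days of screening and baseline before surgery (5.5); follow-up 6 months, plus or minus 1 month (7.1).

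**The plan's own duration.** Last infusion at month n − 1, then 6 months of follow-up, or 7 with the window, plus up to 3 months of screening.
- 4 subjects: 3 + 6 = 9 months, up to 3 + 7 = 10, or 13 with screening.
- 8 subjects: 7 + 6 = 13 months, up to 14, or 17 with screening.

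Both are under two years, so the stated figure is reproduced.

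**Visit window.** 30.4 − 14 = day 16.4 to 30.4 + 14 = day 44.4.

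**Overlap if infusions are exactly one month apart (assumption).** The next infusion is on day 30.4. The share of the window after it is (44.4 − 30.4) / (44.4 − 16.4) = 14/28 = one half. This applies at each of 4 − 1 = 3 transitions, or 8 − 1 = 7. A visit on or before its nominal date does not overlap.

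**Overlap if the spacing varies.** The documents give no distribution, so these figures only show a range.
- Random (Poisson) surgeries at 1 a month: the chance that the next infusion precedes a visit on day V is 1 − exp(−V/30.4). This gives 42%, 63% and 77% per pair for V = 16.4, 30.4 and 44.4. For at least one overlap in 3 pairs, 1 − exp(−3V/30.4) gives 80%, 95% and 99%.
- Monthly consents, surgery uniform over the next 0 to 90 days, visit uniform in its window (200,000 simulations): about 52% per pair and 93% for at least one of 3. About 13% of gaps are under 7 days.
- Slow conversion: section 8.4 says "up to 20 subjects may be consented and screened" to find 4. At 20/4 = 5 consents per treated subject, infusions are about 5 months apart and the one-month visit always comes first.

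**Cost of waiting for the one-month visit.**
- Monthly infusions, visits on or before the nominal date: no delay.
- Monthly infusions, every visit at the end of its window: 14 days × 3 = 42 days, or 6 weeks. The last of 4 infusions moves from month 3.0 to 3 × 44.4/30.4 = 4.4, and the last visit to month 10.4 to 11.4. For 8 subjects the last infusion moves from month 7.0 to 7 × 44.4/30.4 = 10.2, and the last visit to month 16.2 to 17.2.
- Surgeries that would otherwise fall together: up to 44.4 days per transition, and 44.4 × 3 = 133 days, or about 19 weeks. The last infusion is still no later than month 4.4 after the first.

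Adding 3 months of screening to the latest figures gives 14.4 months for 4 subjects and 20.2 for 8, both under 24.

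**The case against.** The best case against is that subjects are watched well before one month. Adverse events are collected from the lumbar puncture (section 9). Patients spend one or two nights in hospital and have a postoperative MRI (5.3.4), and the wound is checked at day 7 to 10 (5.3.5). The PI monitors continuously, at a single centre, and could pause at any time. Infused swine showed no neuronal injury at 24 hours or one month (2.5.3), and section 9.5 rates the risk as minimal.

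Most of this stands, and it limits the point to one scheduled exam. A reader might infer that nobody looks at the subject until one month; the documents do not support that. What remains is that no neurological exam is specified at those earlier contacts, the MRI is there to check electrode position, and none of them is linked to the continuation recommendation. Section 7.2.5 asks for a brief symptom-led physical exam at other assessments, but the inpatient stay and wound check are not in the schedule. Expedited reporting does not close the gap: it covers serious, unexpected events (9.3, 9.4.1), and section 9.5 allows the deficits it lists to be classed as expected.

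It is also fair to object that a wait postpones surgery already planned for clinical reasons. That stands as a cost.

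**Conclusion.** The point holds in a limited form. Following the plan as written permits an infusion before the previous subject's first scheduled full neurological exam, and nothing available for review makes the continuation judgement wait for it. At a monthly infusion pace, half the visit window is exposed at each of 3 transitions, or 7 if the target is 8. That pace is an assumption. Closer surgeries raise the exposure, and slow conversion from consent to surgery could remove it.

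Two stronger readings should be resisted. One is that each later infusion will precede the earlier subject's exam; the documents show only that it can. The other is that this is a first-in-human series: the documents call it a feasibility or pilot study, and the text of section 2.3 (Case Study) was not available for review, so earlier human experience cannot be excluded. The point does not need that label.

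The reassuring animal results and the earlier contacts make this an improvement the sponsor should make, not a fault that undermines the study.

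**What to change.** In sections 8.1 and 9.4.2, state that before each new study infusion the PI records a dated continuation decision based on the previous subject's adverse event data, including the one-month adverse event assessment and neurological exam already scheduled. Set no clinical threshold or stopping rule; the change only fixes when the existing judgement is made and on what data. Reconcile the 4 subjects in section 8.4 with the 8 in section 4.

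The text costs one paragraph and uses existing visits and staff. The time cost for 4 subjects is nil to about 6 weeks at a monthly pace, and up to about 19 weeks if surgeries would otherwise cluster. A wait may postpone a planned operation. It may also mean repeating some baseline assessments under the 90-day limit: in the extreme case where all four subjects were ready on the same day, the fourth could wait 133 days. At the planned recruitment pace, with those recruited going on to treatment, the study still finishes within two years. If all 20 consents were needed at one a month, it would take 19 + 6 = 25 months to 19 + 3 + 7 = 29 months even without this change.

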8.2. Efficacy

The primary efficacy endpoint will be focused on determining the degree of change in motor symptoms as measured from the un-medicated (*off*), UPDRS motor subsection (Part III) at 6 months in comparison to baseline by a movement disorder neurologist.

8.3. Additional Evaluations

Additional measures of safety will be obtained during the study. These secondary measures of safety will include evaluations post-treatment which are compared to a baseline assessment. These measures include:

- Neuropsychological assessment for cognition, depression, and behavioral changes at scheduled visits
- Adverse events
- Physical exam
- Neurological exam

Secondary efficacy endpoints will include comparison of Baseline to post-treatment assessments for:

- Levodopa equivalent medication usage (milligrams)
- Quality of life assessment with PDQ-39

8.4. Statistical Considerations and Sample Size

This is an open-label feasibility study of 4 subjects to be recruited from a single center. In order to find 4 eligible subjects suitable for treatment, up to 20 subjects may be consented and screened. For this study, a statistical sample size analysis is not proposed. All those subjects that were consented and then found not meeting study requirements will be considered screen failures.

The Safety and Effectiveness assessment will be descriptive with no statistical endpoints. The results will be examined and analyzed and used as a basis for determining the nature of future studies.

9. ADVERSE EVENT AND REPORTING

The adverse event collection interval for this study begins at the time of the lumbar puncture (start of investigational procedure) and ends at the 6 Month Follow up visit.

After informed consent has been obtained, and prior to initiation of investigational intervention, only serious adverse events caused by a protocol-mandated intervention should be reported (e.g., serious adverse events related to invasive procedures such as blood draw). AEs reported between the time the patient signed the informed consent and the DBS surgery will be captured as concurrent medical history unless due to a protocol-related procedure.

After initiation of investigational intervention, all adverse events will be reported according to the guidelines in the following sections. After this period, investigators should report any deaths, serious adverse events, or other adverse events of concern that are believed to be related to the investigational intervention.

All adverse events, whether reported by the patient or noted by study personnel, should be recorded in the patient's medical record. Adverse events should be assessed for seriousness, severity, attribute and expectedness by the Principal Investigator, or designee.

AEs should be followed to resolution or stabilization, and reported as SAEs if they become serious. This also applies to subjects experiencing AEs that cause interruption or discontinuation of study intervention, or those experiencing AEs that are present at the end of their participation in the study. Such subjects should receive post-treatment follow-up as appropriate.

If an ongoing AE changes in its severity or in its perceived relationship to study intervention, a new AE entry for the event should be completed.

AE and SAE recording will continue until the End of Treatment visit is performed. SAEs considered related to the interventional procedure may be reported at any time, even after the patient's final visit.

